9.3 Standardization of surgical practice

9.3.1 Principle of Surgical Treatments

9.3.1.1 Anesthesia

The operation is to be carried out with endotracheal intubation under general anesthesia; whether epidural assisted anesthesia is applied or not is left at the discretion of the anesthetist and is not specified in this study protocol.

9.3.1.2 Regulations on punctures and auxiliary incision

The positions of punctures and auxiliary small incision are not specified; the number of punctures should not exceed 5. There should be only one auxiliary small incision whose length shall not exceed the maximum tumor diameter and necessarily will be less than 10 cm in normal cases. If the auxiliary small incision needs to be longer than 10 cm, the surgeon in charge should make a decision and record the reasons in the CRF.

9.3.1.3 Intraoperative exploration

Explore the abdominal cavity for any hepatic, peritoneal, mesenteric, or pelvic metastases and gastric serosal invasion

9.3.1.4 Regulations on the extent of the gastrectomy

Follow the Japanese gastric cancer treatment guidelines 2014 (ver. 4) to perform total gastrectomy under the premise of satisfying the oncological principles.

9.3.1.5 Regulations on the extent of the Lymph node dissection

Follow the Japanese gastric cancer treatment guidelines 2014 (ver. 4): Total gastric resection with D2 Lymphadenectomy (No. 1,2,3,4,5,6,7,8a,9,10,11,12a).

9.3.1.6 Regulations Regarding Greater Omentum Resection

This study protocol requires total greater omentum resection.

9.3.1.7 Regulations Regarding Digestive Tract Reconstruction

The digestive tract reconstruction method is determined by the surgeon according to his/her own experience and the specific intraoperative situation. If instrumental anastomosis is used, the surgeon determines whether manual reinforced stitching of the anastomotic stoma is to be performed; the study protocol does not specify.

9.3.1.8 Regulations Regarding Surgery-related Equipment and Instruments

The energy equipment, vascular ligation method, digestive tract cutting closure, and digestive tract reconstruction instruments are determined by the surgeon responsible for surgery based on experience and actual needs and are not specified in this study protocol.

9.3.1.9 Regulations Regarding Gastric Canal and Peritoneal Drainage Tube

Whether the gastric canal or peritoneal drainage tube is left after surgery is determined by experience and actual needs and is not specified in this study protocol, and record the reasons in the CRF.

9.3.1.10 Regulations Regarding Concurrent Surgical Treatments

If another organ/system disease is present, the responsible surgeon and the relevant department consultants will jointly decide whether a concurrent operation is required and can be performed. The order is determined according to the clinical routine, but these cases will be excluded from the PP set according to the Exclusion Criteria.

9.3.1.11 Regulations Regarding the Processing of Excluded Patients Identified Intraoperatively

If the patient is judged to meet the exclusion requirements during the operation, the study approach will be suspended, and the responsible surgeon will decide upon the subsequent treatment according to the clinical practice of the research center (the therapeutic decision, such as whether to excise the gastric primary focus or metastases, is determined by the responsible surgeon). These cases will be excluded from the PP set according to the Exclusion Criteria.

9.3.1.12 Regulations on conversion to laparotomy

When intra-abdominal hemorrhage, organ damage and other serious/life-threatening complications which are difficult to control occur during robotic surgery, it is necessary to actively convert to laparotomy. If the anesthesiologist and surgeon consider that intraoperative complications caused by carbon dioxide pneumoperitoneum may threaten the patient's life, it is necessary to actively convert to open. The surgeon in charge can decide to convert to laparotomy driven by other technical or equipment reasons and will record said reasons. The reasons for the conversion to open must be clearly recorded in the CRF. The incision length of > 10 cm is defined as a case of

conversion to open surgery in this study.

9.3.2 Operative parameters (same for both groups)

Completed by the research assistant on the day of the operation. specific projects include:

- (1) Name of responsible surgeons
- (2) Operation time (min)
- (3) Type of operation, digestive tract reconstruction, intraoperative damage and whether the tumor was ruptured during surgery (intact rupture of the capsule)
- (4) Length of incision (cm)
- (5) Conversion to open surgery or not and the reasons for this decision
- (6) Intraoperative estimated blood loss (ml; from skin cutting to stitching, intraoperative blood loss = (postoperative gauze weight, grams - preoperative gauze weight, grams) *1ml/g+ suction fluid, ml)
- (7) Blood transfusion (ml): in this study, the blood transfusion event is defined as transfusion of red cell suspension (ml) or whole blood (ml)
- (8) Tumor location
- (9) Tumor size (maximum tumor diameter, mm)
- (10) Number of lymph nodes dissected in each group and distant metastasis (location)
- (11) Proximal resected margin (mm), distal resected margin (mm), radicality(R0/R1/R2)
- (12) Intraoperative complications (occurring from skin incision to skin closure) including:

surgery-related complications: intraoperative hemorrhage and injury: A. Vascular injury: A vascular injury is defined as a blood vessel with either a blood vessel clamp or a titanium clamp closure and an intra-cavity suture or any other method to control the bleeding. B. Organ damage: maybe including diaphragmatic injury, esophageal injury, duodenal injury, colon injury, small intestine injury, spleen injury (excluding <1/3 spleen ischemia), liver injury, pancreatic injury, gallbladder injury, kidney damage etc.

C. Tumor rupture: tumor envelope Integrity damage

air abdominal-related complications: high-blood carbonate, mediastinal emphysema, subcutaneous emphysema, air embolism, respiratory circulation instability caused by abdominal pressure.

Anesthesia-related complications: Allergic reactions.

(13) Intraoperative death (occurring during the time period from skin cutting to skin stitching completion) regardless of reason.

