3.4 Blind method: This research adopts an open design

3.5 Research cycle

Estimated enrollment cycle: complete enrollment within 3 years

Follow-up period: begin at the enrollment of the first case and end 1 month after the enrollment of the last case.

Estimated time: 2018.01.08-2021.01.08(to complete enrollment)- 2021.02.08(to complete follow-up)

4. Study objects

All patients who meet the inclusion criteria and not conform to the exclusion criteria are qualified for this study.

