4.3 Withdraw criteria

- (16) Patients intraoperatively/postoperatively confirmed as T4b
- (17) M1 tumor confirmed intraoperatively or postoperatively: distant metastasis only found by intraoperative exploration or postoperative pathological biopsy or a positive postoperative peritoneal lavage cytology examination
- (18) Requirement of simultaneous surgery for other diseases
- (19) Patients intraoperatively confirmed as unable to complete D2 lymph node dissection/R0 resection due to tumor: unable to complete R0 resection due to regional lymph node integration into a mass or surrounded with important blood vessels, which cannot be resected
- (20) Sudden severe complications during the perioperative period (intolerable surgery or anesthesia), which renders it unsuitable or unfeasible to implement the study treatment protocol as scheduled
- (21) Patients who voluntarily quit or discontinue treatment for personal reasons at any stage after inclusion in this study
- (22) Treatment implemented is proven to violate study protocol.

5. Outcome Measures

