5.2 Secondary Outcome Measures

- Intraoperative morbidity rate
- Operative time
- Estimated blood loss
- Number of harvested and metastatic lymph nodes
- the lengths of incision, proximal and distal margins
- Time to first flatus
- Time to first liquid diet
- Postoperative hospital stay
- Total cost

6. Diagnostic criteria for this study

- (1) The AJCC-8th TNM tumor staging system will be used for this study.
- (2) Diagnostic criteria and classification of gastric cancer: According to the histopathological international diagnostic criteria, classification will be divided into

papillary adenocarcinoma (pap), tubular adenocarcinoma (tub), mucinous adenocarcinoma (muc), signet ring cell carcinoma (sig), and poorly differentiated adenocarcinoma (por).

(3) Definition of advanced stage: tumor infiltration of the stomach wall reaches or exceeds the inherent muscular layer (T2); T2, T3, and T4a patients will be included as study subjects, whereas T4b patients will not.

(4) Definition of esophagogastric junction carcinoma: According to the AJCC-8th tumor staging system, esophagogastric junction carcinoma is defined as a tumor whose tumor center is located within 5cm above and below the esophagogastric junction. According to Siewert classification, the tumor was divided into Siewert type I : the tumor center was located 1 ~ 5 cm above the esophagogastric boundary; Siewert type II : The center of the tumor was 1 cm to 2 cm above the esophagogastric boundary. Siewert type III : The tumor center is located 2 to 5 cm below the esophagogastric boundary. Only Siewert type III esophagogastric junction carcinoma were involved in this study.

7 Qualifications of the participated Surgeons

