111	Above the diaphragm	Lymph gland that is in the cavity of the diaphragm and departs from the gullet (No. 20 that connects to the diaphragm and gullet)
112	Posterior mediastinum	Lymph gland of the posterior mediastinum departed from the gullet and its hiatal portion

血管名

略字説明

APIS *A. phrenica inferior sinistra*
 AGB *Aa. gastricae breves*
 AGES *A. gastroepiploica sinistra*
 VGED *V. gastroepiploica dextra*
 VCDA *V. colica dextra accessoria*
 VCM *V. colica media*
 TGC *Truncus gastrocolicus*
 ACM *A. colica media*
 AJ *A. jejunalis*

AHC *A. hepatica communis*
 VP *V. portae*
 VL *V. lienalis*
 VMS *V. mesenterica superior*
 VPDSA *V. pancreaticoduodenalis superior anterior*
 VCD *V. colica dextra*
 VJ *V. jejunalis*
 AGP *A. gastrica posterior*
 ACD *A. colica dextra*

Fig. 4. Lymph node grouping

(2) Distant metastasis

M0: No distant metastasis outside of the regional lymph nodes

M1: Distant metastasis outside of the regional lymph nodes

MX: Presence of distant metastasis is unclear

Record the specific sites under the M1 condition: peritoneum (PER), liver (HEP), lymph node (LYM), skin (SKI), lung (PUL), bone marrow (MAR), bone (OSS), pleura (PLE), brain (BRA) and meninges (MEN), intraperitoneal exfoliated cells (CY), and others (OTH). Note: A positive examination result for intraperitoneal exfoliated cells is recorded as M1.

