16.2.5.6.2 Radical Records

Postoperative residual tumor, denoted with R (residual tumor): R0: curative resection; R1, R2: non-curative resection.

RX: cannot be evaluated

R0: no residual cancer

R1: microscopic residual cancer (positive margins, peritoneal lavage cytology positive)

R2: macroscopic residual cancer

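### The blood-loss formula adds the whole suction volume as blood, so any non-blood fluid aspirated between incision and closure would be counted as blood loss

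*Protocol*

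**What the plan says.** Section 9.3.2 lists what the research assistant completes on the day of surgery, for both groups alike. Item (6) sets the measurement window, "Intraoperative estimated blood loss (ml; from skin cutting to stitching", and then the rule: "intraoperative blood loss = (postoperative gauze weight, grams - preoperative gauze weight, grams) *1ml/g+ suction fluid, ml". The variable is a secondary outcome in section 5.2 and in the Summary, listed as "Estimated blood loss".

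No item in section 9.3.2 asks for the volume of fluid put into the abdomen or for the volume of ascites. No other section corrects the formula.

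The protocol refers to peritoneal lavage in three ways:

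- Section 4.3, item (17), and the Summary make it a ground for withdrawal: "a positive postoperative peritoneal lavage cytology examination".
- Section 16.2.5.3 uses it for M status: "A positive examination result for intraperitoneal exfoliated cells is recorded as M1".
- Section 16.2.5.6.2 uses it for residual tumour status: "R1: microscopic residual cancer (positive margins, peritoneal lavage cytology positive".

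No section says when the lavage is done, how much fluid is used or where the fluid goes. The section on exploration (9.3.1.3) reads only: "Explore the abdominal cavity for any hepatic, peritoneal, mesenteric, or pelvic metastases and gastric serosal invasion". Irrigation is not mentioned anywhere.

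**The concern.** This is a stated calculation rule, not a detail left open. It treats everything in the suction measurement as blood. If the surgeon aspirates any other fluid before closure, the recorded value is too high by exactly that amount.

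Two consequences follow. If the extra fluid has the same distribution in both groups, both summaries are inflated and the added variation makes a true difference harder to see. If it differs between groups, the difference in fluid passes straight into the difference in blood loss.

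The protocol does not assure equal fluid use. Section 3 describes a non-randomized study, section 3.4 states "This research adopts an open design", and section 9.3.1.8 leaves equipment and instruments to the surgeon.

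A later analysis plan could not repair this by itself, because the volumes needed for the correction are not among the listed items.

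**Working it through.** **Inputs from the protocol.** The formula and window come from section 9.3.2, item (6). The group size of 68 comes from section 3.3; it was derived for postoperative complications and serves here only as a sample size. The protocol gives no mean, SD or expected difference for blood loss, so there is no figure of its own to reproduce.

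**Algebra (no assumption about size).** Let B be true blood loss, whether in gauze or suction. Let F be non-blood fluid that ends in the weighed gauze or the measured suction.

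- Recorded value: R = gauze gain + suction = B + F.
- Error: R − B = F. Each 100 ml of such fluid adds 100 ml.
- Group comparison: mean difference in R = mean difference in B + mean difference in F.
- Spread, if F is independent of B: Var(R) = Var(B) + Var(F).

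**Illustration of one patient (assumed values).** Gauze gain 50 ml and blood in suction 100 ml, so B = 150 ml:

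| F aspirated (ml) | Recorded R (ml) | R / B |
|---|---|---|
| 0 | 150 | 1.0 |
| 100 | 250 | 1.7 |
| 200 | 350 | 2.3 |
| 500 | 650 | 4.3 |
| 1000 | 1150 | 7.7 |

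**Illustration of a difference in fluid use (assumed values).** Equal true blood loss, 68 per group, two-sided 0.05, normal approximation. SE = SD × √(2/68) = 0.1715 × SD. With SD 100 ml and a 50 ml difference in mean F: SE = 17.15, 50/17.15 = 2.92, and Φ(2.92 − 1.96) = 0.83. The probability of a significant but spurious result is:

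| SD of R (ml) | 25 ml difference in F | 50 ml | 100 ml |
|---|---|---|---|
| 100 | 0.31 | 0.83 | about 1.00 |
| 150 | 0.16 | 0.49 | 0.97 |
| 200 | 0.11 | 0.31 | 0.83 |

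**Illustration of noise only (assumed values).** True difference 50 ml, SD of B 100 ml, same fluid distribution in both groups. The SD of R is √(100² + SD_F²):

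| SD of F (ml) | SD of R (ml) | Power |
|---|---|---|
| 0 | 100 | 0.83 |
| 100 | 141 | 0.54 |
| 200 | 224 | 0.26 |
| 300 | 316 | 0.15 |

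**Check of the repair.** Let I be the instilled volume, A the ascites aspirated, and U the part of I that never reaches suction or gauze (left in the abdomen or sent off as a specimen). Then F = (I − U) + A, and the corrected value is R − I − A = B − U.

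Instilled fluid soaked into gauze is therefore dealt with, provided it is subtracted once as part of I and not again at the gauze step. What remains is a downward error of U. The result is negative whenever U exceeds B, so a rule for that case is needed.

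**Reach of the error.** The primary outcome does not use this formula. In section 9.3.2, item (12), intraoperative vascular injury is defined by how bleeding was controlled, not by volume. The 300 ml threshold in the complication table of section 9.3.4 concerns postoperative haemorrhage, which lies outside the formula's window.

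**The case against.** The strongest reply is that the protocol does not show that non-blood fluid ever enters the measured suction. Irrigation is not named, and the surgical rules in section 9.3.1 prescribe no instilled fluid. Section 4.3 calls the lavage cytology postoperative, whereas the blood-loss window ends at skin closure. A cytology sample may also go to a specimen container and never reach the suction measurement. All of this stands. A reader might infer that irrigation and lavage fluid are in fact being recorded as blood loss here; the text supports only the conditional statement that they would be, if aspirated in that window.

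A reader might also infer that blood loss is a main claimed advantage of one approach over the other, which would make the error more serious. Section 1 does not support that for this comparison. The reductions it reports are for laparoscopic against open surgery. Both retrospective series of robotic against laparoscopic total gastrectomy that it describes found no significant difference in blood loss.

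Nor does the protocol show that fluid use differs between groups. The same formula applies to both, so bias in the comparison is a possibility and not a finding. The CRF itself is not shown, so it may already capture instilled volume.

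Finally, plain subtraction is imperfect, because unrecovered fluid pushes the corrected value down. That stands too, and is a reason to state the rule in full.

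None of this removes the core point: the formula has no term for non-blood fluid, and the protocol nowhere supplies one.

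**Conclusion.** The point holds in conditional form. As written, item (6) overstates blood loss by the volume of non-blood fluid collected between incision and closure, millilitre for millilitre. That follows from the formula alone. Whether such fluid is collected in this trial, and how much, cannot be read from the protocol. The tables above therefore show how chosen inputs behave and do not estimate the error here.

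The effect is confined to one secondary outcome. Similar fluid use would inflate both groups and cost precision; different fluid use would bias the comparison. The primary outcome, the non-inferiority margin and the sample size are not affected. Severity is minor to moderate.

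**What to change.** Amend section 9.3.2, item (6), to define blood loss as gauze weight gain (1 ml/g) + (suction volume − irrigation and lavage volume instilled − ascites aspirated). In the same place:

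- State that instilled fluid soaked into gauze is subtracted once only.
- State how unrecovered fluid is handled, for example by setting negative values to zero and reporting how many there were. Fluid sent off as a specimen should be left out of the volume subtracted.
- State that the rule is identical in both groups.

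Add instilled volume and ascites volume to the CRF if they are not already there. Section 11.1.3 gives a route for adding CRF items after the study has started. The formula is protocol text and needs its own amendment.

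For patients already operated on, the correction is possible only if the volumes were recorded elsewhere. Otherwise the report should say that their blood loss is the unadjusted sum.

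The cost is one amended line and one or two recorded fields. Some residual error from incomplete fluid recovery will remain. No surgical step changes.

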9.3.3 Postoperative management

9.3.3.1 The use of prophylactic analgesics

Continuous postoperative prophylactic intravenous analgesia is allowable but not mandatory within postoperative 48 hours; its dose, type and rate of infusion should be determined by the anesthesiologist according to clinical practices and specific patient conditions. The repeated use of prophylactic analgesics is not allowed beyond 48 hours after the end of surgery, unless it is judged necessary

9.3.3.2 Fluid replacement and nutritional support

Postoperative fluid infusion (including glucose, insulin, electrolytes, vitamins, etc.) or nutritional support (enteral/parenteral) will be performed based on doctor's experience and routine clinical practices and is not specified in this study. After oral feeding, it is allowable to stop or gradually reduce fluid infusion/nutritional support.

9.3.3.3 Post-operative rehabilitation management

Management methods of incision, stomach and abdominal drainage tube: Follow regular diagnosis and treatment approaches. Eating recovery time, diet transition strategies: Follow regular diagnosis and treatment approaches.

9.3.3.4 Discharge standard

Patients needed to meet the following criteria for discharge: 1) satisfactory intake of a soft diet. 2) move around of their bed. and 3) absence of complications by routine clinical examinations. This information will be recorded in the CRF.

9.3.4 Postoperative observation items

Definition of "postoperative day n": One day from 0:00 to up to 24:00. Up to 24:00 on the day of surgery is "postoperative day 0;" the next day from 0:00 to up to 24:00 is "postoperative day 1;" and so on. From the first postoperative day until hospital discharge, the research assistant should timely fill in the following items and specific observation items including:

(1) Pathologic results:

Original lesion tissue typing, Distant metastasis, and parts, NIH Hazard grading, Radical surgery degree (R0/R1/R2), The total number of lymph nodes, the number of lymph nodes in each group, the number of lymph node metastases in each group and the total number of metastases in pathological specimens were obtained

(2) Postoperative complications :

Postoperative complications are divided into and short-term complications after surgery and long-term complications after surgery. Short-term is defined as within 30 days of surgery or the first discharge if the hospital days > 30 days. Long-term is defined as the period from 30 days or more after the operation, or the first discharge (the hospital days after surgery >30 days) to 3 years after the operation.

Severity of complication is graded according to Clavien–dindo complication scoring system,¹⁹

IIIA level and above are serious complication

I: Any deviation from the normal postoperative course without the need for pharmacologic treatment or surgical, endoscopic, and radiologic interventions. Allowed therapeutic regimens are drugs as antiemetics, antipyretics, analgesics, and diuretics, and electrolytes and physiotherapy. This grade also includes wound infections opened at the bedside.

II: Requiring pharmacologic treatment with drugs other than such allowed for grade I complications. Blood transfusions and total parenteral nutrition are also included.

III: Requiring surgical, endoscopic, or radiologic intervention

IIIa: Intervention not under general anesthesia

IIIb: Intervention under general anesthesia

IV : Life-threatening complication (including CNS complications) requiring IC(intermediate care)/ICU(intensive care unit) management

IVa: Single organ dysfunction (including dialysis)

IVb: Multiple organ dysfunction

V: Death as a result of complications

Classification and name of complication	Diagnostic criteria
Abdominal bleeding	Intra-abdominal hemorrhage requires blood transfusion, emergency endoscopy or surgical intervention to eliminate anastomotic bleeding
Anastomotic bleeding	The postoperative gastrointestinal decompression tube continued to have fresh red blood outflow; the hemoglobin drops more than 1g/dL
Gastrointestinal anastomotic stoma Fistula	Using gastrointestinal angiography to see contrast agent leak out from the anastomosis, or the blue drainage outflow through tube after oral Methylene blue to eliminate the possibility duodenal stump fistula and

Study protocol

	intestinal fistula
Duodenal Stump Fistula	Using gastrointestinal angiography to see contrast agent leak out from the duodenal stump to eliminate the anastomotic fistula or intestinal fistula
Intestinal fistula	Using gastrointestinal angiography to see the blue drainage outflow through tube after oral Methylene blue to eliminate anastomotic fistula and duodenal stump fistula
Stenosis of Anastomosis	Endoscopic examination with a 9.2-mm endoscopy not passing through the anastomosis to eliminate recurrence of tumors
Input jejunal loop obstruction	Abdominal pain, abdominal distension, vomiting and other symptoms. Abdominal flat to see the right upper abdomen expansion of the intestinal loop, and there is a liquid plane, or a visible input loop jejunum giant expansion by barium meal examination.
Intestinal obstruction after operation	Abdominal X-ray shows a plurality of liquid planes and the phenomenon of intestinal effusion with visible isolated, fixed, swelling of the intestinal loop. Total Abdominal CT showed edema, thickening, adhesion of intestinal wall, accumulation of gas in intestinal cavity, uniform expansion of bowel and intra-abdominal exudation.
Early dumping syndrome	Combined the symptoms of sweating, heat, weakness, dizziness, palpitations, heart swelling feeling, vomiting, abdominal colic or diarrhea with the signs of tachycardia, blood pressure micro-rise, breathing a little faster sign after meal 15-30 minutes, and solid phase radionuclide gastric emptying scanning tips stomach quickly emptying.
Late dumping syndrome	Feeling hungry, flustered, out of sweating 2-3 hours after the meal . Blood sugar is less than 2.9mmol/L, excluding other diseases that cause hypoglycemia
Intestinal ischemia and necrosis	Under the digestive endoscopy, the intestinal mucosa congestion, edema, bruising, mucosal hemorrhage, the mucous membrane being dark red, the vascular network disappearing, can have part mucosal necrosis, following with mucosal shedding, ulcer formation with annular, longitudinal, snake and scattered in the ulcer erosion.
Internal hernia	Postoperative CT findings of cystic or cystic and solid mass, and intestinal aggregation, stretching, translocation, abnormal mesenteric movement, and thickening of the blood vessel.
Alkaline reflux esophagitis	1. Endoscopic examination and biopsy of the upper gastrointestinal

	tract showed evidence of inflammation of the mucous membranes and gastrointestinal metaplasia; 2. CT scan and gastrointestinal barium meal examination showed no expansion or obstruction of the input loop.
Incision splitting	Including partial dehiscence of the incision and full-layer dehiscence
Incisional hernia of abdominal wall	The swelling tumor showing in the surgical scar area or abdominal wall swelling when standing or force. CT shows ventral wall continuity interruption and hernia content extravasation
Incision infection	Thickening of the soft tissue at the incision, in or below the incision of gas, exudation, swelling of the incision or pus from the incision extrusion, or secretion culture of pathogenic bacteria.
Lymphatic leakage	A chyle test when abdominal drainage fluid exceeded 300 ml/day for 5 consecutive days after postoperative day 3.
Pneumonia	Complies with one of the following two diagnostic Criteria: 1. Auscultation/percussion voiced + one of the following: fresh sputum or sputum character changes; blood culture (+); bronchoalveolar lavage fluid, anti-pollution sample brush, biopsy specimens cultured pathogenic bacteria. 2. Chest film hints of new or progressive infiltration + one of the following: fresh sputum or sputum character changes, blood culture (+), bronchoalveolar lavage fluid, anti-pollution sample brush, biopsy specimens cultured pathogenic bacteria; isolate virus or detect IgM, IgG (+) of respiratory viral
Acute pancreatitis	Irritability, abdominal pain, anti-jumping pain, fever, leukocyte increase and blood amylase increased occurring and diagnosed by ultrasound or CT within 3 days after surgery.
Acute cholecystitis	Serum bilirubin exceeding 85 μ mol/l and ultrasound examination shows gallbladder enlargement, wall thickness, signal and sound shadow of gallbladder stone, bile internal sediment, gallbladder contraction bad etc.
Pleural effusion/infection	CT scan showed the localized fluid low density area of thoracic cavity, which could accompany with gas, and culture pathogenic bacteria in thoracic endocrine.
Abdominal infection	There is at least one of the following evidences in abdominal cavity within 30 days after operation: 1. discharge of pus, with/without microbiological examination; 2. bacterial culture positive; 3. diagnosed by detection, pathology, imaging findings.

Study protocol

Pelvic infection	Symptoms of systemic infection or rectal irritation, combined with a rectal finger examination and touching tenderness, or a married woman with a posterior vault to extract pus-based fluid
Sepsis	The following two conditions are available: 1. There is evidence of active bacterial infection, but the blood culture does not necessarily appear pathogenic bacteria; 2. meeting two of the following four items at the same time: (1). body temperature $>39.0^{\circ}\text{C}$ or $<35.5^{\circ}\text{C}$ for 3 consecutive days, (2). heart rate >120 times/min; (3). total white blood cells $>12.0 \times 10^9/\text{L}$ or $<4.0 \times 10^9/\text{L}$, wherein neutrophils >0.80 , or naïve granular cells >0.10 ; (4).Respiratory frequency >28 times/min
Urinary system infection	Symptoms of urine frequency, urgency and urine pain etc. and urine bacteria culture colony count 1000~10 million/ml in the absence of antibiotics; No symptoms of urine frequency, urgency and urine pain etc, urine bacterial culture colony count $\geq 100,000/\text{ml}$
Pancreatic fistula	The level of amylase in the drainage fluid is three times than normal level.
Bile fistula	Symptoms of abdominal distension, Abdominal pain, tenderness, anti-jumping pain, muscle tension, abdominal puncture or drainage fluid for bile
Celiac fistula	The drainage fluid is milky white, and more than 200ml/d and does not decrease for 48 hour, the celiac qualitative test is positive, and the level of triglyceride >110 mg/dL at the same time.
Nutritional disorder after gastrectomy	In the presence of weight loss, anemia, malnutrition bone disease, vitamin A deficiency and other symptoms, laboratory tests suggest that the intestinal absorption function test is abnormal, excluding other causes of nutritional disorders
Bone disease after gastrectomy	Lumbar back pain, length shortening, kyphosis, bone fractures and other symptoms. Bone density decreased combining with elevated alkaline phosphatase and serum calcium reduction, the concentration of serum 25-(OH) D3 and 1,25-(OH) 2D3 increasing and the serum parathyroid hormone increasing. Exclusion of bone disease caused by other causes.
Subcutaneous emphysema	visible the irregular speckle shadow under the skin in the horizontal flat sheet.
Mediastinal emphysema	In the posterior and anterior flat fame, a long narrow gas shadow rises to the neck soft tissue along the mediastinal side, forming a thin-line

	dense shadow. In the lateral flat there was a visible and clear band between the heart and the sternum. The CT examination, if necessary, shows gas density line-like shadow around the mediastinal and mediastinal pleura closing to the direction of the lung field.
Postoperative hemorrhage	An amount of hemorrhage exceeding 300 ml.
Postoperative cardiac dysfunction	The symptom of sinus tachycardia, sinus bradycardia, supraventricular tachycardia, ventricular tachycardia, and other arrhythmias, or heart failure preoperatively none-existing and postoperatively appearing, and other causes of the above-mentioned manifestations are excluded.
Hepatic dysfunction	Bilirubin increasing and the levels of AST and ALT >5 times after operation and these symptoms no existing before surgery,
Kidney function failure	Postoperative continuing renal function insufficiency, blood creatinine rising 2mg/dl, or acute renal failure needing dialysis treatment.
Cerebral embolism	Acute onset, hemiplegia, aphasia and other focal neurological function deficits. Embolism site has low-density infarction, of which border is not clear and no obstructive performance within 24-48 hours after the onset.
Pulmonary embolism	Characteristics of dyspnea, chest pain, syncope, shortness of breath, right ventricular insufficiency and hypotension, pulmonary angiography revealed a filling defect.
Venous thrombosis of lower extremities	Local tenderness, swelling, purple skin color, combined with intravenous angiography to show the filling defect
Mesenteric arterial embolization	Patients with acute abdominal pain, vomiting, diarrhea, abdominal x-ray of intestinal tract filling with gas or existing liquid level, abdominal angiography revealed a filling defect.
DIC	1. There are basic diseases easily leading to DIC, 2. There are more than two clinical performances: (1) severe or multiple bleeding tendencies; (2) Microcirculation disorder or shock cannot be explained by the original disease. (3) Extensive skin mucosal embolism, focal ischemic necrosis, shedding and ulcer formation, or unexplained lung, kidney, brain and another organ failure. (4) anticoagulant treatment is effective. 3. The laboratory meets the following conditions: (1) there are 3 or more experimental abnormalities: platelet count, prothrombin time, activated partial coagulation enzyme time, thrombin time, fibrinogen level, D-two poly, and (2) difficult or special cases for special examination.

Other	Complications other than the above complications, which do not exist before surgery but appear after surgery
-------	--

(1) Blood test items (At postoperative day 1, 3, 5)

Peripheral blood routine assessment: Hb, RBC, WBC, LYM, NEU, NEU%, and PLT、 MONO;

Blood biochemistry: Albumin, prealbumin, total bilirubin, AST, ALT, creatinine, urea nitrogen, fasting blood glucose, potassium, sodium, chlorine, calcium, CRP, IL-6, PCT, Blood amylase, ascites amylase.

(2) Postoperative rehabilitation evaluation:

Time to first ambulation (hours), time to first flatus (hour), time to liquid diet, time to removal of gastric tube (d), daily volume of gastric drainage (ml), time to removal of abdominal drainage tube (d), daily volume of drainage (ml).Blood transfusion volume (ml) from the end of surgery to postoperative discharge: a transfusion event is defined as infusion of the red blood cell suspension (ml) or whole blood (ml).Postoperative hospital stays (days): periods form surgery day to first discharge day

